### 10.3 Management of Adverse Event Reporting

Any adverse events (AEs) and serious adverse events (SAEs) will be recorded in the subject's study record and the Electronic Adverse Event Case Report Form. The following information should be obtained:

- ◆ Description of Adverse Event
- ◆ Onset date
- ◆ Onset time
- ◆ Relationship to device/study as assessed by the investigator (not related, possibly related, probably related)
  - Not related: The adverse event is reasonably expected to be related to (or caused by) a concurrent illness, effect of another device/drug or other cause, and is unlikely related to the investigational product
  - Possibly related: The adverse event is reasonably expected to be related to the investigational product, and an alternative etiology is equally or less likely compared to the potential relationship to investigational product
  - Probably related: There is a strong relationship to investigational product, or recurs on re-challenge, and another etiology is unlikely, or there is no other reasonable medical explanation for the event.
    - Related to device, specify: Investigational or Non-Investigational

**Study Title:** Multi-site Anesthesia randomized controlled Study of End tidal control (Et Control) compared to conventional anesthesia Results (MASTER-Anesthesia Trial)  
**Study No:** 123.07-2015-GE5-0002

GE Healthcare

- Caused by machine failure (yes/no); if yes, indicated type of machine failure
- Relationship to anesthetic agent (yes/no) if yes, provide route of administration of anesthesia
  - Inhaled anesthetic agent
  - Intravenous anesthetic agent
- Relationship to Surgical Procedure (not related, possibly related [describe], probably related [describe])
- Resolution – record date and time of resolution
- Anticipated, Serious, or Unanticipated (yes/no)
  - If Serious Adverse Event or Unanticipated Adverse Device Effect, record date of reporting to Sponsor and IRB.
  - If Serious Adverse Event, record one of the following:
    - Death and date of death
    - Life threatening
    - Significant Disability
    - Hospitalization
    - Congenital anomaly
    - Other, explain
- Outcome – indicate as follows:
  - Ongoing
  - Resolved without sequelae – describe outcome
  - Resolved with sequelae
- Severity (mild, moderate, severe)
  - **Mild:** Symptom(s) barely noticeable to the subject or does not make the subject uncomfortable. The AE does not influence performance or functioning. Prescription drugs are not ordinarily needed for relief of symptom(s).
  - **Moderate:** Symptom(s) of a sufficient severity to make the subject uncomfortable. Performance of daily activities is influenced. Treatment of symptom(s) may be needed.
  - **Severe:** Symptom(s) of a sufficient severity to cause the subject severe discomfort. Treatment for symptom(s) may be given.
- Treatment given and/or action taken (procedure stopped, withdrawn from study, no action, unanticipated ICU admission)

Adverse events will be reported to the local IRB per their policy.

**NOTE:** Adverse events related to NIBP, SpO2, and Heart rate will be reported according to the definition outlined in Section 10.2 – Adverse Event Definitions.

**Study Title:** Multi-site Anesthesia randomized controlled Study of End tidal control (Et Control) compared to conventional anesthesia Results (MASTER-Anesthesia Trial)  
**Study No:** 123.07-2015-GE5-0002

GE Healthcare

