### 3.4.2 Secondary Endpoint:

(1) Efficacy

- a. Response time: time to reach 90% of the desired change in EtAA and  $EtO_2$  steady state mean concentration

**Study Title:** Multi-site Anesthesia randomized controlled Study of End tidal control (Et Control) compared to conventional anesthesia Results (MASTER-Anesthesia Trial)  
**Study No:** 123.07-2015-GE5-0002

GE Healthcare

- b. Settling time: time to achieve the desired EtAA and EtO2 steady state mean concentration
- c. Overshoot amount of the desired EtAA and EtO2 from steady state mean concentration
- d. Accuracy of Et Control in maintaining EtAA and EtO2 control between user set target and steady state end tidal concentrations – For Et Control only. The accuracy measures include percent difference relative to the user set target and percent duration over the steady status with percent difference greater than 5%, 10%, and 15% of the user set target.

**NOTE:** *The response time, settling time, and overshoot amount data extraction will be done in two scenarios: 1) using the algorithmic determination of desired end-tidal concentration of anesthetic agent and oxygen for both arms (see [Appendix 2](#)), and 2) using the clinicians recorded target values of anesthetic agent and oxygen for the Control Arm and using the set target values for the Et Control arm.*

- (2) Safety
  - a. Adverse events (see definition under Section 10.2—[Adverse Event Definitions](#)) will be observed and recorded, the number of events will be counted, and comparison between groups will be performed.

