### 8.1.7 Analysis of Adverse Events

Adverse events will be observed and recorded. Percent of subjects with AEs will be calculated, and comparisons between groups will be performed using Fisher exact test. Number of AEs and AE event rate will also be analyzed using non-parametric Wilcoxon method.

Analysis will be performed for a subset of adverse events of vital sign abnormalities including non-invasive blood pressure (NIBP), SpO2, and heart rate.

In addition, analysis of adverse events will be performed for each subset of patients defined by the pre-existing hypertension (*defined as a patient treated for hypertension*) status and ASA status.

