## 10.2 Adverse Event Definitions

**Adverse Event (AE):** As defined by EN ISO 14155-2011: any untoward medical occurrence, unintended disease or injury, or untoward clinical signs (including abnormal laboratory findings) in subjects, users or other persons, whether or not related to the investigational medical device.

**NOTE:** *This definition includes events related to the investigational medical device or the comparator. This definition includes events related to the procedures involved.*

Given the frequency at which physiological changes occur during the course of general anesthesia, the following definitions for changes in blood pressure, heart rate, and oxygenation will be used to determine adverse event reporting. If any of the parameters reach the below thresholds they shall be reported to the Sponsor as adverse events.

- (1) **Non-Invasive Blood pressure (NIBP):** defined as having the systolic blood pressure (SBP) reading < 70 mmHg or > 160 mmHg or mean arterial pressure (MAP) of < 55 mmHg or > 120 mmHg for > 5 minutes.
- (2) **Peripheral Capillary Oxygen Saturation (SpO2):** defined as having a value less than 90% for more than 5 minutes.
- (3) **Heart rate:** defined as the heart rate < 45bpm or > 110bpm for more than 5 minutes.

Additional adverse events related to physiological changes can be reported at the clinician's discretion.

**Serious Adverse Event (SAE):** As defined by EN ISO 14155-2011: an adverse event that

- a. led to death;
- b. led to a serious deterioration in the health of the subject, that either resulted in:
  - (1) a life-threatening illness or injury, or
  - (2) a permanent impairment of a body structure or a body function, or
  - (3) in-patient or prolonged hospitalization, or
  - (4) medical or surgical intervention to prevent life-threatening illness or injury or permanent impairment to body structure or a body function;
- c. led to fetal distress, fetal death, or a congenital abnormality or birth defect.

**NOTE:** *Planned hospitalization for a pre-existing condition, or a procedure required by the Clinical Investigation Plan (clinical protocol), without serious deterioration in health, is not considered a serious adverse event.*

**Anticipated Adverse Device Effect:** Any adverse event and/or reaction, the specificity or severity of which is consistent with the IRB approved informed consent, protocol, investigator brochure, or product labeling.

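### Section 8.1.7 compares vital-sign adverse events by occurrence, number and rate only, so it cannot see an arm difference in depth, or in duration beyond 5 minutes

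*Combined protocol and SAP*

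**What the plan says.** - **Safety endpoint (3.4.2).** For adverse events, "the number of events will be counted, and comparison between groups will be performed".
- **Analysis (8.1.7).** Occurrence is handled first: "Percent of subjects with AEs will be calculated, and comparisons between groups will be performed using Fisher exact test". For frequency, the section then plans a rank test: "Number of AEs and AE event rate will also be analyzed using non-parametric Wilcoxon method". The section adds a vital-sign subset and splits by hypertension and ASA status, but names no measure of severity, depth or duration.
- **Event definition (10.2).** The limits are SBP below 70 or above 160 mmHg, MAP below 55 or above 120 mmHg, SpO2 below 90%, and heart rate below 45 or above 110 bpm, each for more than 5 minutes. "If any of the parameters reach the below thresholds they shall be reported to the Sponsor as adverse events".
- **Severity (10.3).** Mild opens "Symptom(s) barely noticeable to the subject or does not make the subject uncomfortable" and adds no effect on functioning and no usual need for prescription drugs. Moderate refers to discomfort, daily activities and possible treatment. Severe reads "Symptom(s) of a sufficient severity to cause the subject severe discomfort. Treatment for symptom(s) may be given". No grade refers to a recorded value or a duration.
- **Data collected.** Section 6.3.2 takes vital signs from the EMR at least every 2.5 minutes for 2 hours, then at least every 5 minutes. Section 10.3 records onset and resolution times.
- **Related provisions.** Section 8.1.8 compares vasoactive drug use by type, reason, number of subjects and total dose. Section 11.1 lists MAP below 55 mmHg or SpO2 below 90% for more than 10 minutes among its early-termination criteria. Under section 13, two early terminations pause enrollment and convene the DSMB.

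**The concern.** Table 10-1 ties hypotension to excessive agent delivery, hypertension to insufficient agent delivery, and hypoxia to insufficient oxygen delivery. A delivery problem in one arm could show as deeper or longer excursions as well as more of them. A count treats a 30-minute episode as one event and two 6-minute episodes as two, so it can even rank the arms the wrong way round on time spent beyond a limit.

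The severity grade would be the natural second source, but it does not fit these events. All nine adverse events in the feasibility study (1.2.3) were hypotension treated with medication. For such an event under anesthesia, the opening of Mild is met because nothing is felt, its sentence on prescription drugs points the other way, and Moderate and Severe both require discomfort. Investigators are unblinded (4.2), so improvised grading is also open to bias.

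The study supports a marketing application (3.1), and section 1.3.1 expects an equivalent safety profile. Counts alone cannot support that expectation for depth or for duration past the threshold.

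**Working it through.** **1. The plan's own figure.** The only figure borrowed is the 124 per arm in Table 8-1. For EtAA the standardized effect is (5 + 3)/16 = 0.5. At one-sided 0.025 and power 0.95 the t-test needs 105 per arm, and 105/0.85 = 123.5, which rounds up to 124. It reproduces and is not in dispute.

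**2. What section 8 compares.** Section 8.1.7 uses occurrence, number and rate. Section 8.1.9 summarizes gas concentrations within 10 minutes of an event, not the subject's vital signs. No part of section 8 compares blood pressure, SpO2 or heart-rate values between arms.

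**3. Illustration: assumptions.** The documents give no event durations, so these inputs are assumed:
- 124 per arm; at most one event per subject; the same event probability p in both arms.
- p = 0.30, range 0.20 to 0.40. The feasibility study reports 6 events among 15 subjects (6/15 = 40%) and 3 among 13 (3/13 = 23%). These are events, not subjects, and that study's event threshold is not stated.
- Duration = 5 minutes plus an exponential excess.

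**4. Total durations averaging 8 versus 16 minutes** (excess 3 versus 11), zeros included:
- Means per subject: 0.30 × 8 = 2.4 and 0.30 × 16 = 4.8, a difference of 2.4 minutes.
- Variances: 0.30 × (8² + 3²) − 2.4² = 16.1, and 0.30 × (16² + 11²) − 4.8² = 90.1.
- SE = √((16.1 + 90.1)/124) = 0.93; 2.4/0.93 = 2.6; approximate power Φ(2.6 − 1.96) ≈ 74%.
- Simulation with Welch's test gives about 76%, and about 53% and 92% at p = 0.20 and 0.40. Fisher on any event and Wilcoxon on counts stay at about 3 to 5%.

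**5. The same 8 versus 16 read as excess over 5 minutes:**
- Means: 0.30 × 13 = 3.9 and 0.30 × 21 = 6.3, again a difference of 2.4 minutes.
- Variances: 0.30 × (13² + 8²) − 3.9² = 54.7, and 0.30 × (21² + 16²) − 6.3² = 169.4.
- SE = √(224.1/124) = 1.34; 2.4/1.34 = 1.79; Φ(1.79 − 1.96) ≈ 43%. Simulation gives about 42%.

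**6. Choice of statistic.** With excess means of 5 versus 10 minutes and p = 10%, 25% and 40%, a Wilcoxon test of minutes with zeros included rejects in only 5%, 6% and 14% of runs, because the tied zeros dominate. Restricted to subjects with events it rejects in 27%, 63% and 82%, but that comparison conditions on a post-randomization outcome. A difference in means over all subjects avoids both problems.

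**7. When counts do respond.** If episode lengths are exponential with mean m, the share lasting over 5 minutes is exp(−5/m). Doubling m from 2.5, 5 or 10 minutes moves that share from 14% to 37%, 37% to 61%, or 61% to 78%.

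**The case against.** A reader might infer that a harmful device would show no difference anywhere in the plan. The documents do not support that.
- Section 8.1.8 compares vasoactive total dose and reason by arm, and 6.3.2 lists hypotension and anesthetic overdose as reasons. Deeper or longer hypotension can show there.
- In the case of step 4, 124 × 0.30 × exp(−5/11) ≈ 24 Et Control subjects and 124 × 0.30 × exp(−5/3) ≈ 7 control subjects would exceed 10 minutes. If the events were low MAP or desaturation, the provisions in 11.1 and 13 would bring that to the DSMB.
- The suspected cause, faulty delivery, is measured directly by the primary endpoints and by the overshoot and deviation analyses in 8.1.4.1.
- Step 7 shows that longer episodes usually raise the count as well.

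All of this stands, and it narrows the point without closing it. Successful treatment can mask depth. Desaturation has no counterpart to 8.1.8. Sections 11.1 and 13 are monitoring rules rather than an arm comparison, and their vital-sign criteria do not cover heart rate or high pressure.

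A reader might also infer that the severity grades will give false reassurance, or that a long low-MAP event would be graded Mild. No severity table is planned and 8.1.7 uses no grade, so the wording feeds no named comparison. A treated event also does not meet Mild as a whole. What remains is that the scale cannot be applied consistently under anesthesia.

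**Conclusion.** The gap is confined to 8.1.7. Among events past the 5-minute threshold it cannot distinguish the arms on depth or on further duration, and the rest of the plan covers this only indirectly. The poor fit of the 10.3 severity wording is a secondary matter.

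The figures of about 76% (total durations) and about 42% (excess over 5 minutes) are illustrations. They rest on assumed durations and on equal incidence, and equal incidence guarantees that the count tests reject at no more than about the nominal 5%. Depth was not simulated. The simulation used Welch's test on events longer than 5 minutes, not the bootstrap interval on all minutes beyond a limit that is proposed below. The case for the change is that it is cheap and adds information. It does not show that the trial's safety conclusion would fail.

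**What to change.** **Section 8.1.7.** For each existing 10.2 limit, low and high separately, derive each subject's minutes beyond the limit and worst value from the EMR vital signs and the recorded onset and resolution times. Report the arm difference in mean minutes with a bootstrap 95% confidence interval, zeros included, beside the counts, and show worst values by arm. Label this a supportive safety analysis. The low SBP limit is 70 mmHg in 10.2 and 75 mmHg in the section 18 glossary; the two must be reconciled before programming.

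**Section 10.3.** State that vital-sign events during anesthesia are described by recorded duration and worst value, leaving any grading cut-offs to the sponsor. Keep the discomfort scale for awake PACU and 24-hour events.

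**Cost.** A few derived variables and a wording change in the eCRF guidance, with no new data, visits or subjects. Minutes are coarse at 2.5- to 5-minute sampling, clinicians may change the sampling interval when a subject is unstable, and a mean is sensitive to a few long events. Those limits are the reason to use a bootstrap interval and to keep the counts alongside.

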#### 10.4 Management of Serious Adverse Event and Unanticipated Adverse Device Effect Reporting

All SAEs and/or UADEs will be documented as above and reported in writing to the Sponsor within 72 hours of knowledge of the event. The Investigator shall submit the Adverse Event eCRF and GEHC\_GQP\_10.07.005\_F002 Site Notification and Assessment of Serious and Unexpected Adverse Events (DOC0910335) with redacted supporting documentation to SAE mailbox. If the event resulted in the death of a subject, the event shall also be reported via telephone to the Sponsor within 24 hours of knowledge of the event. SAEs will be reported to the local IRB per their policy.

UADEs shall be reported by the investigator to the IRB as soon as possible but no later than 10 working days per 21 CFR 812.140(a)(1). GE Healthcare, as study Sponsor, shall investigate and report any UADEs to FDA, all participating principal investigators and IRBs within 10 working days from receiving notice of the UADE from the Investigator per 21 CFR 812.150(b)(1).

#### 10.5 Follow-up and Use of Collected Data of Subjects with Reported Event

Subjects with reported event (AE, SAE, ADE, SADE, UADE, or USADE) shall be followed until the resolution of the event. The Investigator shall submit a follow-up report as indicated in the above-mentioned section.

If an event occurred during the study procedure and the subject was withdrawn or discontinued as deemed necessary by the Investigator, any data collected up to the resolution of the event may be used by the Sponsor for the assessment of the event.

#### 10.6 Management of Device Complaints

Any complaints regarding the operation of the device or software or any malfunctions are to be reported to the Sponsor Clinical Affairs Project Manager (CAPM).

## 11. EARLY TERMINATION OR SUSPENSION

### 11.1 Early Termination of Subjects

Early termination of a subject is defined as any situation in which the clinician determines they no longer want to continue with the case, or the clinician may choose to discontinue the Et Control mode during a case. The following objective criteria are utilized to determine when it is appropriate to terminate the subject's participation in the study; additionally, to terminate the Et Control in the investigational arm:

- Mean arterial pressure of less than 55 mmHg that is sustained for greater than 10 minutes; OR
- SpO2 less than 90% that is sustained for greater than 10 minutes; OR
- With respect to device performance, the Et Control device is not meeting the expected performance requirements such that:
  - Measured EtO2% is less than 21% for 5 min; OR
  - Measured ETAA% at steady state deviates from the set EtAA% by more than the following:
    - Desflurane +/- 2.0 % for 5 min
    - Sevoflurane +/- 0.6 % for 5 min
    - Isoflurane +/- 0.3 % for 5 min
- An unrecoverable failure that prevents the use of Et control (*Unrecoverable failure is defined as the inability to use Et Control mode because of unrecoverable device malfunction*)

The reason for early termination will be recorded on the Electronic Case Report Form.

If the Et Control system detects any issues or fault conditions during the case (such as leaks or accuracy issues), the Et Control program may temporarily transition to fall back mode or enter fresh gas mode until the clinician is able to address and resolve the issue. *This is not considered early termination.* This is a design element to help mitigate potential safety risks and correct failure modes.

Cases in which there are brief periods of use outside of Et Control based on the algorithm self-exiting will continue to be analyzed as part of the Et Control Arm.

### 11.2 Criteria for Early Termination or Suspension of the Study

The Sponsor has established a criterion for stopping/pausing enrollment in this study:

- Three (3) subjects in the Et Control Arm of the study have a serious adverse event (SAE) or an unanticipated adverse device effect (UADE) at any point in the study.

**Study Title:** Multi-site Anesthesia randomized controlled Study of End tidal control (Et Control) compared to conventional anesthesia Results (MASTER-Anesthesia Trial)  
**Study No:** 123.07-2015-GE5-0002

GE Healthcare

If this criterion is met, the enrollment in the study will be paused (placed on hold) and the study sites, IRB, and FDA will be notified. An IDE Supplement may be submitted to FDA to discuss resuming enrollment.

In addition to the above, the DSMB may make recommendations to terminate the study or enrollment for other observed safety concerns on the basis of their clinical judgment. The Sponsor is responsible for final decision regarding early termination of the study based on DSMB recommendations.

Also, the study may be terminated early if the Sponsor determines that unanticipated adverse event(s) presents an unreasonable risk to subjects or for any other reason as Sponsor determines to be appropriate.

Termination shall occur no later than 5 working days after the Sponsor makes the determination and no later than 15 working days after Sponsor first received notice of the effect.

The Sponsor will promptly notify the Investigators of any determination to terminate the study outside of the protocol timeframe. The Sponsor will provide each Investigator with written guidelines/instructions on termination processes and timelines.

The Investigator is responsible for reporting the early termination to their local IRB.

### 11.3 Follow-up and Use of Collected Data of Subjects Withdrawn/Discontinued

A 24-hour follow-up will be conducted for subjects that were withdrawn or were discontinued from study participation during the study procedure. Assessment of adverse events and intraoperative awareness shall be collected [see Section 6.3.4—Twenty-four (24) hour Follow-up Post PACU data collection], and shall utilize the Electronic Adverse Events and Intra-Operative Awareness Questionnaire electronic case report forms (eCRFs). No additional follow-up will be conducted for subjects that withdrew or were withdrawn from study participation prior to study procedure.

Any data collected during the participation of the subject or prior to withdrawal will still be included in the study results and provided to the Sponsor.

## 12. INSTITUTIONAL REVIEW BOARD (IRB) AND REGULATORY FILINGS

### 12.1 Regulatory Authority Approval Requirements

This study will be conducted in the U.S. and will comply with the Medical Device Good Clinical Practice regulations promulgated pursuant to the Food, Drug, and Cosmetic Act, including 21 CFR Parts 11, 50, 54, 56, and 812. The regulatory authority which governs this clinical trial is the U.S. Food and Drug Administration. Significant risk device clinical investigations require

**Study Title:** Multi-site Anesthesia randomized controlled Study of End tidal control (Et Control) compared to conventional anesthesia Results (MASTER-Anesthesia Trial)  
**Study No:** 123.07-2015-GES-0002

GE Healthcare

prior FDA approval of an Investigational Device Exemption and approval by participating Institutional Review Boards.

